## 8.2.6 Actual Treatment

The subjects' actual treatment will be derived from exposure data. If a subject receives a study treatment that is different from the planned treatment for the entire time of treatment, then actual treatment is the treatment actually received. In the event that a subject receives both CSL346 and placebo, the subject will be included in the CSL346 group for this analysis set. Subjects receiving only placebo will be included in the placebo group.

## 8.2.7 Derived Variables

### **Derivation of Body Mass Index (BMI)**

BMI will be calculated using the following formula:

$$\text{BMI (kg/m}^2\text{)} = \text{Weight (kg)} / [\text{Height (m)}]^2$$

using the height measured at Screening and the weight measured at Day 1 (if available). If weight at Day 1 is not available, the assessment prior to IP administration available closest to Day 1 will be employed.

### **Derivation of ACR**

For the purposes of the analysis of ACR, baseline will be defined as the geometric mean of the 6 values obtained before treatment (3 values from Visit 3 and 3 values immediately before treatment at Visit 4). ACR (mg/g) will be derived from first morning void (FMV) urine samples.

On-treatment assessments of ACR will be the geometric mean values from multiple FMV collections (3 FMV collections, except Visit 9 where only 2 FMV samples will be collected) at each time point.

The ACR will be provided with the lab data. Only the geometric mean values for analysis purpose will be calculated.

### **Derivation of eGFR**

eGFR will be derived using the following the Chronic Kidney Disease Epidemiology Collaboration (CKD-EPI) formula [[Levey et al. 2009](#)]:

$$\text{eGFR} = 141 \times \min(\text{Scr}/\kappa, 1)^\alpha \times \max(\text{Scr}/\kappa, 1)^{-1.209} \times 0.993^{\text{Age}} \times 1.018 \text{ [if female]} \times 1.159 \text{ [if black]},$$

where Scr is serum creatinine,  $\kappa$  is 0.7 for females and 0.9 for males,  $\alpha$  is -0.329 for females and -0.411 for males, min indicates the minimum of Scr/ $\kappa$  or 1, and max indicates the maximum of Scr/ $\kappa$  or 1.

The standardized serum creatinine (SCr) is expressed as mg/dL. The years of age will be for all eGFR calculations the years of age collected by eCRF. “Black” will be accounted as race of “Black or African American”.

### 8.3 Stratification and Covariates

Stratification of subjects at enrollment will be based on whether subjects are receiving concomitant treatment with an SGLT2i. At least 50% of the subjects enrolled are to be receiving an SGLT2i. The analysis will include this stratification term in the model and results by these subgroups will be reported.

### 8.4 Study Periods Relative to Treatment

All data will be assigned to one of the four study time periods defined below.

**Screening** is defined as the time from signing of the informed consent form through Visit 2.

The **Lead-in Period** is defined as the time Post-Visit 2 (from SC saline test infusion) up to subject randomization.

The **Treatment Period** is defined as the time from randomization through Visit 9 (12 weeks after the first administration of IP).

**Follow-up** begins after the last administration of IP at Visit 9 through the EOS visit 12 weeks later.

## 9 Study Population

Unless otherwise stated, all tables and listings in [Sections 9.1 – 9.4](#) will be based on the ITT analysis set.

### 9.1 Subject Disposition

The following summaries will be provided for the Screened Analysis Set by each CSL346 group (8 mg/kg or 16 mg/kg) as well as combined over CSL346 groups, placebo and total population for:

- Subjects who underwent Screening – only total;
- Screening failures with reason for failure – only total;
- Subjects eligible for randomization – only total;
- Subjects not eligible for randomization and reason for being not eligible– only total;
- Subjects randomized – by treatment and total;
- Subjects randomized but not treated – by treatment and total;
- Subjects treated – by treatment and total;

- Subjects treated who completed through the final efficacy assessment at Week 16 – by treatment and total;
- Subjects treated who discontinued from the study before the final efficacy assessment at Week 16 with reason – by treatment and total;
- Subjects treated who completed the study at Week 24 – by treatment and total;
- Subjects treated who discontinued from the study before Week 24 with reason – by treatment and total;
- Subjects entering and discontinuing each period of the study (screening, lead-in, treatment, follow-up);
- Subjects in each of the analysis sets described in [Section 6](#).

The disposition summary will be given by study period and in addition stratified by:

- Subjects in each stratum for SGLT2i (obtained from IRT data);
- Subjects defined by level of eGFR at baseline (20-45, 45 - <60, 60 - <90, ≥90 mL/min/1.73m^2);
- Subjects defined by level of ACR by 24 hr. urine at baseline (30 - ≤300, >300 - ≤1000 and >1000 mg/g).

Disposition events related to COVID-19 will also be presented by counts and percentages.

Reasons for study discontinuation will be presented in the order they are displayed in the CRF.

By-subject listing will be provided for disposition status for each subject. This will include:

- Randomization scheme based on the ITT Analysis Set;
- Subject disposition with date of screening (in case of re-screening, all screening records will be listed), date (and time) of the randomization, date (and time) of first IP administration, Week 16 date, Week 24 date, and date of completion/withdrawal;
- Screening failures with reason;
- Subjects who discontinued from the study with reason for discontinuation.

## 9.2 Protocol Deviations

A protocol deviation occurs when an investigator site, or study subject, does not adhere to protocol-stipulated requirements. Deviations will be assessed by CSL as they are reported and then evaluated periodically during study conduct, based on protocol deviation plan for this study developed by CSL Behring.

Deviations will be categorized as either major or minor. Major protocol deviations for subjects in the ITT Analysis Set and Per-Protocol Analysis Set will be summarized for

number and percentage of subjects with each protocol deviation, though all major and minor deviations will be listed. In addition, a summary of violations of inclusion, exclusion, and randomization criteria will be provided for ITT Analysis Set and Per-Protocol Analysis Set.

The final decision regarding protocol deviations and assignment of subjects to analysis population will be made during the blinded data review meeting.

The following by-subject listings will be provided based on the Screened Analysis Set:

- All protocol deviations (including inclusion and exclusion criteria violations, and violations of randomization criteria);
- Subject assignment to analysis sets and reasons for exclusion.

### **9.3 Demographic and Baseline Characteristics**

Descriptive statistics as specified in [Section 7](#) will be provided for continuous variables, number and percentage of subjects for categorical variables.

The following summaries will be provided for the ITT and Per-Protocol Analysis Set:

- Demographic characteristics (e.g. age, race, ethnicity, sex, baseline height, and baseline body weight, and BMI). In addition to summarization as a continuous variable, age will also be categorized and summarized by <25, 25 to ≤45, >45 to ≤65, >65 years. Country will be summarized by number and percentage of subjects in USA, Australia, New Zealand;
- Disease characteristics including the duration since diagnosis of Type II diabetes mellitus (T2DM) to enrollment in the screening period of the study, duration of albuminuria to enrollment, ACR (30 - ≤300, >300 - ≤1000 and >1000 mg/g), SGLT2i status (obtained from IRT data), eGFR status 20 - <45, 45 - <60, 60 - <90, ≥90 mL/min/1.73m^2), signs and symptoms of diabetes (e.g. diabetic retinopathy, autonomic neuropathy, peripheral diabetic neuropathy, diabetic ketoacidosis, diabetic foot ulcer, other diabetic neuropathy, other active skin ulcer), family history of diabetes (e.g. family history of type 1 diabetes, family history of type 2 diabetes)
- Medical history (coded using MedDRA – the MedDRA version will be populated in the tables output) will be presented by system organ class (SOC) and PT.

In addition, demographics will be provided stratified by SGLT2i presence, baseline eGFR and baseline ACR.

Corresponding by-subject listings will be provided. The listing for disease characteristics will include but is not limited to the year of diagnosis as well as the duration for T2DM. The

medical history listing will also provide an indicator of whether the condition was active at the time of entry into the screening period.

## 9.4 Prior/Concomitant Medications

Prior/concomitant medications will be coded using World Health Organization Drug Dictionary Enhanced (WHO-DDE) B3. The version will be populated in the table output.

The reported medication will be classified as 'Prior' or 'Concomitant' as follows. Note that a drug which is administered both before and after the first dose of study medication will fall into both 'Prior' and 'Concomitant' categories.

- 'Prior': if the subject has not taken any IP; or if the medication start date [/time] is before IP start date [/time]. Note that this period will include the screening and lead-in periods of the study;
- 'Concomitant' if the medication end date is after the IP start date [time]. Note this includes the treatment and follow-up periods of the study;
- If the medication start date or end date are partially or completely missing, the medication will be assigned to both 'Prior' and 'Concomitant' unless there is clear evidence that the medication stopped before IP start date (that is, the medication should be assigned only to 'Prior') or that the medication started after IP start date [/time] (that is, the medication should be assigned only to 'Concomitant').

Prior and Concomitant medications will be summarized separately showing the number and percentage of subjects taking concomitant medications by Anatomical Therapeutic Chemical (ATC) classification level 4 and PT. If the ATC level 4 coding is not available for a PT, the next available lower level ATC code will be used. Summaries of Prior and Concomitant medications will be based upon either the Safety Analysis Set or the Per Protocol Analysis Set.

Counts of the number of subjects with prior and concomitant therapies will be presented in tabular form. Counts of the number of subjects on all therapies considered standard of care will be provided separately with special note of changes in dose during concomitant treatment, refer to [Appendix 16.3](#) for standard of care therapies. As a change in a standard of care therapy the following will be accounted:

- Any new concomitant therapy;
- Any change in dose or route or frequency of an existing therapy.

A further summary will provide treatments associated with COVID-19. Those medications will be identified by CSL Behring and a respective flag will be given in SDTM data sets, provided by CSL Behring.

The following listing will be provided:

- Prior and concomitant medication.

## **10 Efficacy Analyses**

Data for the primary endpoint, ACR, as well as serum creatinine, eGFR, blood pressure and some biomarkers will be collected multiple times after the initiation of treatment, therefore, the primary analysis for these outcomes will be a mixed effects model repeated measures (MMRM) approach. The change from baseline to Weeks 2, 4, 8, 12, 16, and 24 will be included in the model.

Biomarkers of lipid metabolism, glycemic control and novel biomarkers of kidney function will also employ a model similar to the primary endpoint (with the exception of biomarkers measured only at the beginning and end of the study). Exploratory biomarkers will be the subject of a separate report.

### **10.1 Analysis of Primary Endpoint(s)**

#### **10.1.1 Primary Estimand**

The primary interest is to quantify the treatment effect of CSL346 under the situation where SGLT2i may be a possible effect modifier and is included in the model. The estimand for the ITT Analysis Set is the average effect of CSL346 on the geometric mean ACR at 16 weeks averaged across subjects receiving and not receiving SGLT2i. All data collected through Week 24 will be used in the analysis.

The primary estimand in line with the primary interest of the study is described as follows:

- Treatment Condition: four SC administrations of CSL346 or placebo over a 12-week period (Day 1, Weeks 4, 8 and 12) where the primary comparison is between CSL346 at Week 16, regardless of dose, and placebo, while subjects have not died. The “treatment policy strategy” will be used, i.e. changes in dose, for example from 16 mg/kg to 8 mg/kg OR the number of subcutaneous injections, or treatment discontinuation/non-initiation, or other miscellaneous factors influencing ACR will not be taken into account in the primary analysis;
- Population: the target patient population defined by T2DM and DKD and further eligibility criteria;

- Variable: change from baseline at 16 weeks of log ACR;
- Population-level summary: difference in treatments, calculated as  $100\% \times (\text{geometric mean ratio of the treatment comparison} - 1)$  based on log ACR.

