### 10.1.2 Primary Efficacy Analysis

The primary analysis is a mixed effects model, repeated measures (MMRM) analysis of the change from baseline through 24 weeks of log ACR, with the primary treatment comparison at Week 16 (Visit 10). The model will include treatment (at 3 levels: 8 mg/kg CSL346, 16 mg/kg CSL346, and placebo), baseline log ACR, the stratification variable related to the concomitant use of SGLT2i, visit (as a categorical factor), and interactions between visit and each of the other model terms as factors. The primary comparison of interest will be calculated using a contrast of  $0.5 (8 \text{ mg/kg CSL346} + 16 \text{ mg/kg CSL346}) - \text{Placebo}$ . Please see [Section 16.1](#) for the corresponding SAS Code for the MMRM model. Because this is an early development study and the first study in subjects with T2DM, the one-sided alpha level to be employed for this test is 0.10. Estimated treatment effect of individual CSL346 dose levels versus placebo will also be summarized. The treatment comparisons will be expressed as a percent difference in treatments, calculated as  $100\% \times (\text{geometric mean ratio of the treatment comparison} - 1)$ . The covariance matrix structure to be employed in the primary analysis will be an unstructured pattern. In the event of model convergence issue, a Toeplitz heterogeneous structure will be employed. If the model still fails to converge an autoregressive structure ARH(1) will be assumed.

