#### **10.1.4 Subgroup Analyses of Primary Endpoint(s)**

Two a priori subgroup analyses to be considered will be based on the strata defined by the presence or absence of concomitant use of a SGLT2i and by eGFR status at baseline (20 - <45, 45 - <60, 60 - <90,  $\geq 90$  mL/min/1.73m^2). Each subgroup will be analyzed in a similar manner as the primary analysis as a mixed effects model, repeated measures (MMRM) analysis of the change from baseline through 24 weeks of log ACR, with the primary treatment comparison at Week 16 (Visit 10). The model will include treatment, baseline log ACR, and interactions between visit and each of the other model terms as factors. For subgroup analysis by SGLT2i, the factor of SGLT2i is not to be included in the model. Scatterplots of ACR and/or change in ACR by eGFR will also be provided.

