## 16 Appendices

### 16.1 SAS Code

SAS code for MMRM analysis

```
Ods graphics on;
Proc mixed data=data_set method=reml plots=residualpanel;
  Class treatment visit patient sglti_yn;
  Model chglnacr =treatment visit baseline sglti_yn
  treatment*visit sglti_yn*visit baseline*visit / alpha=0.20 cl
  ddfm=kr covb solution;
  Repeated visit / type=un subject=patient r rcorr;

* *** Estimate for treatment difference at 2 weeks *** *;
  Estimate "CSL08 vs. PBO at 2 weeks" treatment 1 0 -1
  treatment*visit 1 0 0 0 0 0      0 0 0 0 0 0      -1 0 0 0 0 0 / CL
  alpha=0.2;
  ESTIMATE "CSL16 vs. PBO at 2 weeks" treatment 0 1 -1
  treatment*visit 0 0 0 0 0 0      1 0 0 0 0 0      -1 0 0 0 0 0 / CL
  alpha=0.2;
  ESTIMATE "CSL vs. PBO at 2 weeks" treatment 0.5 0.5 -1
  treatment*visit 0.5 0 0 0 0 0      0.5 0 0 0 0 0      -1 0 0 0 0 0 / CL
  alpha=0.2;

* *** Estimate for treatment difference at 16 weeks *** *;
  Estimate "CSL08 vs. PBO at 16 weeks" treatment 1 0 -1
  treatment*visit 0 0 0 0 1 0      0 0 0 0 0 0      0 0 0 0 -1 0 / CL
  alpha=0.2;
  ESTIMATE "CSL16 vs. PBO at 16 weeks" treatment 0 1 -1
  treatment*visit 0 0 0 0 0 0      0 0 0 0 1 0      0 0 0 0 -1 0 / CL
  alpha=0.2;
  ESTIMATE "CSL vs. PBO at 16 weeks" treatment 0.5 0.5 -1
  treatment*visit 0 0 0 0 0.5 0      0 0 0 0 0.5 0      0 0 0 0 -1 0 / CL
  alpha=0.2;

  Lsmmeans treatment treatment*visit / diff cl;
run;
Ods graphics off;
```

Where:

- chglnacr is the repeated measure of change in log ACR collected at Weeks 2, 4, 8, 12, 16 and 24;
- treatment takes on three levels (CSL346 8 mg/kg, CSL346 16 mg/kg and placebo)

- sglt2i\_yn is the stratification variable associated with the presence or absence of a concomitant SGLT2i at entry into the trial;
- baseline is the baseline log ACR used as a covariate in the model;
- visit is the time variable;

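### SAP 10.1.1 calls SGLT2 inhibitor use a possible effect modifier, but no planned analysis estimates or tests whether the treatment effect differs by SGLT2i use or by eGFR

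*SAP*

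**What the plan says.** SAP 10.1.1 states the primary interest as the effect of CSL346 where "SGLT2i may be a possible effect modifier and is included in the model". It defines the target as an effect "averaged across subjects receiving and not receiving SGLT2i".

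SAP 10.1.2 lists treatment, baseline log ACR, the SGLT2i stratification variable and visit, plus "interactions between visit and each of the other model terms as factors". The code in SAP 16.1 gives the interaction terms as "treatment*visit sglti_yn*visit baseline*visit". Treatment therefore interacts with visit and with nothing else. Protocol 10.3.2 specifies the same model.

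SAP 8.3 adds: "The analysis will include this stratification term in the model and results by these subgroups will be reported".

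SAP 10.1.4 names two a priori subgroup factors: SGLT2i use, and baseline eGFR in four categories (20 to < 45, 45 to < 60, 60 to < 90, >= 90). "Each subgroup will be analyzed in a similar manner as the primary analysis", and "For subgroup analysis by SGLT2i, the factor of SGLT2i is not to be included in the model". Scatterplots of ACR or its change against eGFR are also planned. SAP 8.2.3 says baseline eGFR will define covariates, but no specified model contains eGFR.

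**The concern.** A factor modifies an effect when the treatment difference depends on its level. A model without a treatment-by-SGLT2i term cannot express that, because at each visit it gives one treatment difference for users and non-users alike. Calling SGLT2i a possible effect modifier that is in the model may lead a reader to think modification is being assessed.

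The subgroup section does not fill the gap. It yields two SGLT2i results and four eGFR results, each with its own Week 16 comparison, but no difference between them, no interval for a difference and no homogeneity test. The other analyses do not help: the secondary and biomarker models have the same structure, and the Cochran-Mantel-Haenszel test of albuminuria category only stratifies by SGLT2i.

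SGLT2i use is the only stratification factor, with a 50% enrolment floor. Enrolment by eGFR is staged so that the population comes closer to the one intended for phase 3 (Protocol 3.1). The subgroup results are therefore likely to be read for development decisions. With only separate results to hand, the easy comparison is which subgroup reached significance, and that is a poor guide to whether effects differ.

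**Working it through.** **Inputs.** SAP 4.4: SD 0.65 for the change in ln(ACR); 27% reduction, so delta = ln(0.73) = -0.315; one-sided alpha 0.10; 94 evaluable subjects split equally between pooled CSL346 and placebo. SAP 8.3: at least 50% on SGLT2i. Protocol 4.1.1: at least 36 subjects with eGFR < 60 and at least 18 with eGFR < 45, if the IDMC endorses their inclusion.

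**The plan's own figure.** n per arm = 2(1.282 + 1.036)² × 0.65² / 0.315², which rounds up to 46, or 92 in total against the stated 94. With 47 per arm, SE = 0.65 × sqrt(2/47) = 0.134 and power is 85.4% (noncentral t, 92 df). The smallest significant effect is 1.291 × 0.134 = 0.173, or -15.9%. The SAP's 85%, -0.173 and -16% are reproduced.

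**Separate SGLT2i fits, same true effect in both strata** (assumed 47/47, arms balanced within strata):
- SE per stratum = 0.65 × sqrt(4/47) = 0.190.
- Power per stratum = 64.2% (noncentral t; 64.7% by normal approximation).
- P(exactly one significant) = 2 × 0.642 × 0.358 = 46.0%. A simulation of 200,000 trials under the normal approximation gave 45.6%.
- With 70% on SGLT2i (an assumed upper end), powers are 75.2% and 50.2%, and the discordance is 0.752 × 0.498 + 0.502 × 0.248 = 49.9%.

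**Separate eGFR fits, same true effect throughout.** If the minimums are just met, the two lowest categories hold 18 each (36 - 18 = 18). The plan gives no split above 60, so 32/32 is assumed. Scaling all four by 0.94 for the 94 evaluable subjects gives 16.9/16.9/30.1/30.1:
- Power per category is 39% in the smaller two and 52% in the larger two.
- All four significant: 4%. None: 9%. A mixture: 87%.
- P(a point estimate favours placebo) = Φ(-0.315/0.316) = 16% in each smaller category and Φ(-0.315/0.237) = 9% in each larger one. At least one: 1 - 0.84² × 0.908² = 42%.
- At 1:1:2, 18 subjects give 18/4 = 4.5 per active dose.

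**What a joint estimate would give.** SE of the difference in effects = sqrt(SE1² + SE2²).
- SGLT2i 47/47: sqrt(2) × 0.190 = 0.268, twice the overall SE of 0.134. The 80% half-width is 1.282 × 0.268 = 0.344, and exp(0.344) = 1.41, so the ratio of the two geometric mean ratios is known within a factor of 1.41 either way.
- Power for a difference as large as the whole planned effect (0.315): Φ(0.315/0.268 - 1.282) = 46% at one-sided 0.10, and 32% at two-sided 0.10.
- With 70% on SGLT2i: SE 0.293, power 42% at one-sided 0.10.
- eGFR < 60 versus >= 60 (36:64, scaled to 94): SE 0.279, power 44% at one-sided 0.10. Separate fits on this split would be discordant in 48% of trials with no true difference.

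These figures use a completer-type SE with equal SD in every subgroup and take no credit for baseline adjustment or repeated measures.

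**The case against.** **No listed objective asks whether SGLT2i use or eGFR changes the effect, and the estimand is an average.** This stands. A reader might infer that the primary analysis is misspecified or misses its estimand. The documents do not support that: an average effect remains meaningful under modification, and because randomization is stratified by SGLT2i, the main-effects contrast approximates a size-weighted average over the strata. In 10.1.1 the problem is wording.

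**The subgroups do not overlap, so anyone can difference the separate estimates by hand.** True: z = (d1 - d2)/sqrt(SE1² + SE2²). It would be too strong to say that separate fits cannot show a difference. The accurate statement is that the SAP does not plan to estimate or report it.

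**An unstructured matrix for six visits has 6 × 7/2 = 21 parameters, which looks unworkable in about 18 subjects.** SAP 10.1.2 provides fallbacks on non-convergence: heterogeneous Toeplitz (6 + 5 = 11 parameters), then ARH(1) (6 + 1 = 7). These reasonably carry over to 10.1.4, so the plan is not stuck. If the fallback is invoked one subgroup at a time, the fits being compared could rest on different covariance structures.

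**eGFR is never called an effect modifier, and scatterplots against it are planned.** Correct. The eGFR part rests on 10.1.4 and 8.2.3, not on the estimand. The scatterplots are useful but give no estimate of how the treatment effect varies with eGFR.

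**SAP 10.1.4 does not tell anyone to compare significance across subgroups.** Also correct. The 46% measures how often that tempting comparison would mislead, not an error rate of a prescribed test.

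**Conclusion.** The point holds in a limited form. SAP 10.1.1 says more about SGLT2i than the model delivers, and as planned no analysis estimates or tests whether the effect differs by SGLT2i use or eGFR. The primary test, its error rate and the sample size are unaffected.

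Under one common effect, SGLT2i strata would disagree on significance in about 46% of trials at a 50:50 split and about 50% at 70:30. The four-category eGFR figures illustrate the same problem but rest on an assumed split and on minimums that apply only with IDMC endorsement.

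A joint analysis would not settle the matter. At this sample size it would miss an SGLT2i difference as large as the whole planned effect more often than not, so a null interaction must not be read as evidence of a uniform effect. Its value is to put the right quantity, with its uncertainty, in front of the reader. This is a cheap improvement that should be made, not a flaw in the primary analysis.

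**What to change.** - **Primary analysis:** keep the model, contrast and sample size. Reword SAP 10.1.1 to say that SGLT2i is adjusted for as the stratification factor.
- **SAP 10.1.4:** replace the separate fits with one MMRM per factor on the ITT set, adding subgroup, subgroup-by-visit, treatment-by-subgroup and treatment-by-subgroup-by-visit, with a common covariance matrix. For SGLT2i, the first two terms are already in the primary model.
- **Reporting:** from each joint model, give the Week 16 pooled CSL346 versus placebo effect within each subgroup and the difference between those effects with an 80% CI, labelled exploratory.
- **eGFR:** base the interaction on < 60 versus >= 60, the split SAP 11.2 already uses for TEAEs, or on continuous eGFR. A joint model with all four categories would have 3 × 4 × 6 = 72 treatment-by-category-by-visit cells and would keep the 4 to 5 subjects per active dose in the smallest groups.
- **Caution to add:** a null interaction does not show homogeneity. An 80% CI will also exclude no difference in about 20% of trials where there is none.

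The cost is SAP wording and a few lines of code. The statistical price is assuming a common covariance matrix, and a common baseline slope at each visit, across subgroups.
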